## 8.5. Electrocardiograms

A 12-lead ECG will be performed at the time points specified in Table 1 after the patient has been resting in a supine position for 10 minutes. The Day 1 pre-dose ECG must be reviewed by the Investigator or their designee before dosing to ensure that there are no clinically significant findings that would prevent dosing. Additional ECGs may be performed at the discretion of the Investigator or when clinically indicated.

If a patient has an abnormal value ECG at Screening for either of the parts of the study, the ECG may be repeated twice. If after the second repeat measurement the value does not qualify the patient, he or she is not eligible for dosing. If the patient has prolongation of the QTc interval or any arrhythmia during the post-dose ECGs, no further lefamulin should be administered.

#### **8.6.** Pharmacokinetics

## **8.6.1.** Plasma Sample Collection

Blood samples will be taken for the measurement of PK parameters at the following time points in each part of the study (Table 1):

• Pre-dose; 30 min, and 1, 1.5, 2, 4, 8, 12, and 24 hours post-dose.

For details on sample collection, preparation, and shipment, refer to the study-specific Laboratory Manual supplied by the Sponsor. It is recommended that the blood samples are taken by a venipuncture or from a separate catheter, other than the catheter used for the infusion, to prevent any contamination of the PK blood samples with lefamulin from the infusion line and catheter.

Plasma samples will be analyzed for concentrations of lefamulin and its metabolite BC-8041 using a validated liquid chromatography-tandem mass spectrometry (LC-MS/MS) method at the bioanalytical laboratory.

The maximum total blood volume collected in the study for safety and PK evaluations is 36 mL per patient.

#### **8.6.2. Sputum Sample Collection**

Spontaneous sputum samples will be collected first thing in the morning on Day 1 (pre-dose), and as many times as possible that the patient can provide a sample until 24 hours after dosing for PK analysis of lefamulin. The exact time of sputum production will be recorded so the post-dose time can be determined precisely.

Any spontaneous production of sputum during inpatient observation will also be collected and the time of collection documented.

For details on sample collection, preparation, and shipment, refer to the study specific Laboratory Manual supplied by the Sponsor.

Sputum samples will be analyzed for concentrations of lefamulin using a validated LC-MS/MS method at the bioanalytical laboratory.

#### 8.7. Prior and Concomitant Medications

Prior and concomitant medications, including prescription medications, dietary supplements/vitamins, and over-the-counter medications will be recorded in the eCRF throughout the study. Topical medications will be recorded only if used as treatment for an adverse event. At a minimum, the drug name (preferably generic), dose, frequency, indication, and the start and stop dates of administration should be recorded.

Medications will be coded using the current version of the World Health Organization (WHO) Drug Dictionary.

#### 8.7.1. Prior Medications

All medications taken within 14 days before Day -1 of the first treatment administration will be recorded in the eCRF.

02 November 2021 31 Confidential

#### **8.7.2.** Concomitant Medications

All medications (other than study drug) taken from Day 1 through the Follow-up Visit after the second dosing period will be recorded in the eCRF, including any medications used to treat an adverse event.

## 8.8. Restrictions During the Study

The following restrictions apply to all patients.

- No grapefruit, grapefruit juice, grapefruit products, pomelo, or Seville oranges from 24 hours before Day 1 until discharge from CRU in each part of the study.
- No excessive alcohol consumption (> 21 g alcohol per day for men and > 14 g alcohol per day for women) or use of alcohol from 48 hours before Day 1 until discharge from CRU in each part of the the study.
- No use of vaporized nicotine or cannabidiol products, smoking (regularly or intermittently) more than 5 cigarettes (or equivalent) per day, or any use of tobacco other than in cigarettes or cigars within 28 days of Day 1 through discharge from the CRU.

## 8.9. Discontinuation from Study Medication

Patients are free to withdraw from study medication at any time for any reason. Patients may be withdrawn from study medication at the discretion of the Investigator at any time. If a patient is discontinued from study medication, the reason for discontinuation will be collected in the eCRF.

A patient will be discontinued prematurely from the study medication for any of the following reasons:

- Patient request
- Lost to follow-up
- Death
- Physician decision (ie, assessment that it is not in the patient's best interest to continue, or other reason)
- Sponsor decision
- Positive drug/alcohol test
- Failure to meet eligibility criteria either part of the study

If a patient is prematurely discontinued from study medication, the Investigator should obtain a PK sample if possible and perform all procedures scheduled for discharge from the unit. The patient will be contacted for a Follow-up phone call 4 to 7 days from the time he/she is discharged from the unit to ensure the ongoing wellbeing of the patient. If a patient reports any AEs which represent a cause for concern, he/she will be required to attend the clinic for a Follow-up assessment. This will be considered an unscheduled visit. Any patient withdrawn from study medication due to an adverse event or clinically significant abnormal laboratory test

result will be evaluated by the Investigator, or a monitoring physician, and will be treated and/or followed until the symptoms or values have either resolved or are assessed as stable by the Investigator.

## 8.10. Discontinuation from Study

Patients are free to withdraw from the study at any time for any reason. Patients may be withdrawn from the study at the discretion of the Investigator at any time. If a patient is discontinued from the study, the reason for discontinuation will be collected in the eCRF.

A patient may be discontinued prematurely from the study for the following reasons:

- Withdrawal of consent by patient
- Adverse event
- Pregnancy
- Lost to follow-up
- Death
- Other (to be specified by the Investigator)

If a patient is prematurely discontinued from the study, the Investigator should obtain a PK sample if possible and perform all procedures scheduled for discharge from the unit. The patient will be contacted for a Follow-up phone call 4 to 7 days from the time he/she is discharged from the unit to ensure the ongoing wellbeing of the patient. If a patient reports any AEs which represent a cause for concern, he/she will be required to attend the clinic for a Follow-up assessment. This will be considered an unscheduled visit. Any patient withdrawn from study medication due to an adverse event or clinically significant abnormal laboratory test result will be evaluated by the Investigator, or a monitoring physician, and will be treated and/or followed until the symptoms or values have either resolved or are assessed as stable by the Investigator.

Every reasonable attempt should be made to retain patients in the study. If a patient does not report to the study site for a scheduled visit, study personnel will make 3 contact attempts: 2 telephone contact attempts and, if these are unsuccessful, a certified letter will be sent to the patient. The patient will be considered lost to follow-up if: (1) upon receipt of delivery confirmation of the certified letter the patient does not contact the site; or (2) the certified letter is returned as undeliverable.

#### 9. ADVERSE EVENTS

#### 9.1. Definition of Adverse Events

An AE is any untoward medical occurrence in a patient or clinical investigation patient administered a pharmaceutical product and which does not necessarily have a causal relationship with this treatment. An AE can therefore be any unfavorable and unintended sign (including an abnormal laboratory finding), symptom, or disease temporally associated with the use of a medicinal (investigational) product, whether or not related to the investigational medicinal product.

Any pre-existing conditions or signs and/or symptoms present in a patient before the start of the study (ie, before informed consent) should be recorded as medical/surgical history. Any medical occurrences that are new or worsened from the time of informed consent and up to and including the final visit must be reported as AEs. All AEs must be recorded regardless of causality.

Patients will be monitored throughout the study for adverse reactions to the study medications and/or procedures at each study visit. Questions will be posed in a non-leading manner so as not to bias the response. In addition to questioning at specific time points, patients will be encouraged to spontaneously report any AEs. Any patient with an AE or clinically significant abnormal laboratory test result will be evaluated by the Investigator, or a monitoring physician, and will be treated and/or followed until the symptoms or values have resolved or are assessed as stable by the Investigator. A physician, either at the investigative site or at a nearby hospital emergency room, will administer treatment for any serious adverse events (SAEs). When appropriate, medical tests and examinations may be performed to ensure an AE has fully resolved.

Adverse events will be collected throughout the study from the time a patient signs the informed consent through the Follow-up assessment after the second dosing period. Whenever possible, a specific disease or syndrome rather than individual associated signs and symptoms should be identified by the Investigator and recorded on the eCRF. However, if an observed or reported sign or symptom is not considered a component of a specific disease or syndrome by the Investigator, it should be recorded as a separate AE on the eCRF.

The Investigator will evaluate and report the onset date/time, outcome and end date/time, severity (intensity), relationship to study drug, actions taken with study drug, whether event caused study discontinuation, whether concomitant or additional treatment was given, and determination of seriousness for each AE.

Laboratory abnormalities will not be considered AEs unless they are associated with clinical signs and symptoms or require medical intervention. Clinically significant abnormal clinical laboratory findings, unless judged by the Investigator as more severe than expected for the patient's condition, or that are present or detected at the start of the study and do not worsen, will not be reported as AEs.

The Investigator will exercise medical and scientific judgment in deciding whether an abnormal clinical laboratory finding or other abnormal assessment is clinically significant.

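### Section 9.1 has two conflicting laboratory AE tests with no order of precedence; one excludes symptom-free, clinically significant abnormalities that need no intervention

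*Protocol*

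**What the plan says.** Section 9.1 of the protocol deals with laboratory results in three places.

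- **General definition and duty to report.** The definition reads "An AE can therefore be any unfavorable and unintended sign (including an abnormal laboratory finding), symptom, or disease temporally associated" (with use of a medicinal product). The next paragraph adds a duty of AE reporting: "Any medical occurrences that are new or worsened from the time of informed consent and up to and including the final visit must be reported". Neither sentence sets a condition about symptoms or intervention.
- **First laboratory sentence.** "Laboratory abnormalities will not be considered AEs unless they are associated with clinical signs and symptoms or require medical intervention". Clinical significance plays no part in this test.
- **Second laboratory sentence, directly after it.** It opens "Clinically significant abnormal clinical laboratory findings, unless judged by the Investigator as more severe than expected for the patient's condition" and ends "or that are present or detected at the start of the study and do not worsen, will not be reported as AEs". Symptoms and intervention play no part in this test.

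The section then leaves it to the investigator's judgment "in deciding whether an abnormal clinical laboratory finding or other abnormal assessment is clinically significant", without saying what that decision means for AE status. Section 8.4 also has the investigator grade out-of-range results, and calls for repeat testing of unexpected significant ones, but does not mention AE recording. Section 8.3 does give such a link for vital signs.

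Section 11.6 defines a TEAE as an AE that starts at or after dosing. Section 4.2.2 lists TEAEs as a secondary endpoint, alongside laboratory assessments.

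**The concern.** Narrowing a broad AE definition for laboratory values is common practice and would be no error by itself. The difficulty is that the two narrowing sentences apply different tests and nothing says which governs. The second also reads as though words have been lost. Taken literally, it makes non-reporting the default for the findings an investigator considers clinically significant.

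What is at stake is consistent recording. The synopsis plans approximately 6 sites, and Section 8.4 uses local laboratories. Each site would have to settle the conflict for itself, and the same result could be an AE at one site and not at another. A statistical analysis plan cannot repair this, because it can only analyse the AEs that sites have recorded.

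**Working it through.** The protocol gives no figure to reproduce here, so the check is to apply each rule to the same set of cases.

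**Cases.** Take a laboratory finding that the investigator judges clinically significant and that is new or worsened after consent. Three yes/no factors appear in the rules: symptoms, need for intervention, and severity beyond what the patient's condition would predict. That gives 2 × 2 × 2 = 8 combinations.

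**Reading.** Each 'unless' is first read in the ordinary way, so that meeting the exception makes the finding an AE.

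| Case | Symptoms | Needs intervention | Worse than expected | General text | Laboratory sentence 1 | Laboratory sentence 2 |
|---|---|---|---|---|---|---|
| 1 | no | no | no | AE | not AE | not AE |
| 2 | no | no | yes | AE | not AE | AE |
| 3 | no | yes | no | AE | AE | not AE |
| 4 | no | yes | yes | AE | AE | AE |
| 5 | yes | no | no | AE | AE | not AE |
| 6 | yes | no | yes | AE | AE | AE |
| 7 | yes | yes | no | AE | AE | not AE |
| 8 | yes | yes | yes | AE | AE | AE |

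**Results.**
- The two laboratory sentences give opposite answers in cases 2, 3, 5 and 7: 4 of 8. The conflict runs both ways. In case 2 only sentence 2 reports the finding; in cases 3, 5 and 7 only sentence 1 does.
- The general text conflicts with sentence 1 in cases 1 and 2: 2 of 8.
- At least two of the three rules disagree in cases 1, 2, 3, 5 and 7: 5 of 8.
- Among the four symptom-free cases, sentence 1 excludes two (1 and 2), sentence 2 excludes two (1 and 3), and both exclude only case 1.

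**Stricter reading.** Suppose instead that the two sentences are cumulative exclusions, so that a finding must escape both. Sentence 1 excludes 2 cases, sentence 2 excludes 4, and they share 1, so 2 + 4 − 1 = 5 of 8 are excluded. The two sentences then no longer contradict each other, but together they withhold five kinds of new, clinically significant finding that the general text requires to be reported.

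These are counts of logical combinations, not probabilities.

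**Where it reaches the outputs.**
- *TEAE counts.* AE status comes first (Section 11.6). With the target of 12 patients (Section 11.1), one reclassified patient changes an incidence by 1/12 = 8.3 percentage points, provided all 12 receive that treatment and the patient is not already counted in that row of the table.
- *TEAEs leading to discontinuation.* Sections 8.9 and 8.10 name an AE and a clinically significant laboratory result as separate grounds for withdrawal. Under sentence 1, a patient withdrawn for a symptom-free result that needs no intervention has no TEAE to display.
- *Serious TEAEs.* The 24-hour reporting duty in Section 9.4 is explained as covering any AE that meets a serious criterion, and blood dyscrasias are among that section's examples. A symptom-free blood abnormality needing no intervention could fail sentence 1 before seriousness is considered.

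**The case against.** The best defence is that there is no strict contradiction. The general definition says only that a laboratory finding can be an AE, and a specific rule may narrow a general one. Both laboratory sentences say what will not be an AE; neither says that meeting its exception is enough. On that view they simply add up. This has force against the 4-of-8 count, which depends on the ordinary reading of 'unless'. It does not remove the problem: the cumulative reading collides with the mandatory sentence on new or worsened occurrences, and the text does not tell a site which reading to use.

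The defence is fully right about several stronger conclusions that a reader might draw:

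- *That unrecorded abnormalities would not be followed up.* Section 9.1 requires patients with a clinically significant laboratory result to be evaluated, and treated or followed until it resolves or stabilises, whether or not it is an AE.
- *That such results vanish from safety reporting.* Laboratory assessments are their own secondary endpoint, and Section 11.6 provides summaries, change from baseline and individual patient listings. In 12 patients a large rise would be visible there.
- *That only one panel follows each dose.* In the synopsis, the Follow-up Visit after the first period doubles as Screening for the second, and chemistry and hematology are due at Screening and Day -1. Day -1 tests can be skipped only when Screening was within 72 hours (Table 1, footnote b). After the second dose, though, the 24-hour panel is followed only by a phone call unless a visit is thought necessary.
- *That every symptom-free abnormality is kept out.* Sentence 1 still admits those that need intervention, and sentence 2 does not withhold those worse than expected.

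**Conclusion.** The point stands as a defect in AE recording. Two adjacent laboratory rules in Section 9.1 use different tests, have no order of precedence and do not fit the section's general reporting duty; no other section reconciles them. A new, symptom-free finding that needs no intervention but is worse than expected is out under one sentence and reportable under the next. A finding with symptoms or a need for intervention, but no worse than expected, is the reverse.

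The effect is limited to TEAE counts, the displays of serious TEAEs and of TEAEs leading to discontinuation, and consistency across sites. The 8.3 points is simply the weight of one patient in 12. The protocol gives no basis for estimating how many patients would be affected, and the safety analysis is descriptive.

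The conclusion assumes that a new or worsened laboratory abnormality counts as a medical occurrence under the general text, which that text's express mention of laboratory findings supports. The 4-of-8 count also assumes the ordinary reading of 'unless'; on the cumulative reading, the conflict is with the general text in 5 of 8 combinations.

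**What to change.** Before data collection, merge the general text and the two laboratory sentences of Section 9.1 into one laboratory AE rule for all sites. It should state how clinical significance, symptoms, need for intervention and severity relative to the patient's condition combine. It should keep the existing exclusion of findings that were there at the start and have not worsened.

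One wording that keeps all of the protocol's own criteria: a new or worsened laboratory abnormality is an AE if it causes symptoms, or requires intervention, or is judged both clinically significant and more severe than the patient's condition would predict. Under this rule cases 2 to 8 in the table are AEs and case 1 is not. The sponsor may set the threshold elsewhere, provided that there is a single rule and the general reporting sentence is made to defer to it. Section 8.4 should refer to the same rule.

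The cost is one rewritten paragraph, a cross-reference and possibly a few more AE records. Sample size, visit schedule and analyses do not change.

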## 9.2. Assessment of Severity (Intensity)

The following definitions for rating severity (intensity) will be used:

- **Mild**: An AE that is usually transient and may require only minimal treatment or therapeutic intervention. The event does not generally interfere with usual activities of daily living.
- **Moderate**: An AE that is usually alleviated with specific therapeutic intervention. The event interferes with usual activities of daily living, causing discomfort but the patient is still able to function.
- **Severe**: An AE that interrupts usual activities of daily living, or significantly affects clinical status, or may require intensive therapeutic intervention.

02 November 2021 34 Confidential

## 9.3. Assessment of Relationship to Study Drug

The Investigator will use his/her clinical judgment to explain each AE and determine its relationship, if any, to study drug treatment. Alternative causes, such as natural history of the underlying diseases, concomitant therapy, other risk factors, and the temporal relationship of the event to the study drug will be considered and investigated. The Investigator will also consult the Investigator's Brochure in the determination of his/her assessment. Causality should be assessed using the following categories:

- **Not related:** The event could readily be explained by factors not involving the study drug and a temporal relationship with the study drug did not exist.
- **Possibly Related:** There was some temporal relationship between the event and the administration of the study drug and the event was unlikely to be explained by the patient's medical condition or other therapies.
- **Probably Related:** The temporal relationship between the event and the administration of the study drug was suggestive, and the event was less likely to be explained by the patient's medical condition or other therapies.
- **Definitely Related:** The event followed a reasonable temporal sequence from administration of the study drug, followed a known or suspected response pattern to the study drug, was confirmed by improvement upon stopping the study drug (dechallenge) and reappeared upon repeated exposure (rechallenge). (NOTE: this is not to be construed as requiring re-exposure of the patient, however, a category of definitely related could only be used when recurrence was observed.).

#### 9.4. Serious Adverse Events

An SAE is any untoward medical occurrence that:

- Results in death.
- Is life-threatening. NOTE: The term 'life-threatening' in the definition of "serious" refers to an event in which the patient was at risk of death at the time of the event; it does not refer to an event which hypothetically might have caused death if it was more severe.
- Results in persistent or significant disability/incapacity.
- Requires inpatient hospitalization or prolongation of existing hospitalization.

NOTE: Hospitalizations, which are the result of elective or previously scheduled surgery for preexisting conditions, which have not worsened after entry into the study, should not be classified as SAEs. For example, admission for a previously scheduled ventral hernia repair would not be classified as an SAE; however, complication(s) resulting from a hospitalization for an elective or previously scheduled surgery that meet(s) serious criteria must be reported as SAE(s).

- Is a congenital anomaly/birth defect.
- Is an important medical event.

[figure not shown]
NOTE: Medical or scientific judgment should be exercised in deciding whether reporting is appropriate in other situations, such as important medical events that may not be immediately life threatening or result in death or hospitalization but may jeopardize the patient or may require medical or surgical intervention to prevent 1 of the other outcomes listed in the above definition. These should also be considered serious. Examples of such events are invasive or malignant cancers, intensive treatment in an emergency room or at home for allergic bronchospasm, blood dyscrasias, or convulsions that do not result in hospitalization, or development of drug dependency or drug abuse.

All SAEs occurring from the time of informed consent through completion of the Follow-up assessment after the second dosing period must be reported to Nabriva Therapeutics DAC or their representative within 24 hours of the knowledge of the occurrence (this refers to any AE that meets 1 or more of the aforementioned serious criteria). Reporting is done by completing the SAE form electronically in the Electronic Data Capture (EDC) system or paper SAE report form, whichever is applicable. The EDC system and/or paper report forms should be completed in as much detail as possible but lack of complete information should not delay the reporting of the SAE.

There may be situations in which an SAE has occurred and the Investigator has minimal information to include in the initial report to Nabriva Therapeutics DAC, or their representative. However, it is very important that the Investigator always makes an assessment of causality for every event prior to transmission of the SAE report form to Nabriva Therapeutics DAC, or their representative. The Investigator may change his/her opinion of causality in light of follow-up information, amending the SAE report form accordingly. The causality assessment is 1 of the criteria used when determining regulatory reporting requirements.

The Investigator will provide the assessment of causality per instructions on the SAE form in the eCRF. Serious AEs determined by the Investigator to be related to the study drug must be reported even if more than 30 days after the last administration of study drug have elapsed. In addition, the Sponsor will also assess causality of SAEs based on the information provided by the Investigator.

All SAEs and suspected unexpected serious adverse events (SUSARs) will be reported by the Sponsor to the relevant competent authorities in accordance with the European Directive 2001/20/EC, as applicable.

